### **Primary analysis**

Primary analysis of Repeated Measures Analysis (RMA) Model will be performed for above secondary efficacy endpoints above as given in the Section [5.2.2](#).

### **Secondary analysis**

Secondary analysis of ANCOVA model will be performed to test the significance of treatment difference for secondary efficacy endpoints above as given in the Section [5.2.2](#).

### **Additional analysis**

Summary analysis will be performed to compare difference between baseline to Week 4, Week 8, Week 16, Week 24, Week 32, Week 42 and Week 52, a paired t-test performed for secondary efficacy endpoints above as given in the Section [5.2.2](#).

To further evaluate if the improvements are clinically relevant, effect size of the treatment difference at Week 4, Week 8, Week 16, Week 24, Week 32, Week 42 and Week 52, Cohen's d will also be calculated for the secondary efficacy endpoints as given in the Section [5.2.2](#).

## **5.3.2. Safety Analyses**

The safety analyses will be based on the Safety analysis set, unless otherwise specified.

### **5.3.2.1. Extent of Exposure**

- Number of days of exposure to study drug will be calculated based on the formula:  
**Duration of Exposure in Weeks = (Treatment stop date – Treatment start date)/7**
- Duration will be summarized by treatment group. Each subject will contribute duration of exposure to the treatment taken.
- Participants who were randomized but not report a treatment start date will be categorised as having zero days of exposure.

A listing and summary table of exposure will be created.

The details of the planned displays are in programming specification document.

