7. Visually confirm temperature tape is in biohazard bag and is within range (2° - 8° C), document compliance.
8. Visually confirm syringe is closed with cap.
9. Remove syringe from bag and begin mixing syringe, gently rocking back and as well as rolling between hands, bringing the study treatment to room temp, and suspending them into a homogenous solution. No particulates should be visible.
10. Inject the contents into a 250cc bag of normal saline for injection
11. Properly label the infusion bag with the subject ID, D.O.B, preparation date, time and expiration and cover it with an amber bag.

Once, the study treatment has been mixed by the unblinded pharmacist following the above procedures, the infusion nurse or designated study staff will administer the study treatment as follows:

1. Confirm that the subject number and DOB placed on the amber bag label belong to the subject receiving the infusion.
2. Administer the infusion solution over a period of 1h (infusion rate 4-5ml/min).
3. Do not store or reuse any unused portion of the infusion solution. Any unused product or waste material should be disposed in a biohazard container.
4. Complete the source documents of the visit to accurately collect the start and end times of the infusion and add comments if necessary.
5. The study's subject will be monitored for a total of 2 hours from drug exposure to discharge.
 - During the Investigational product administration (1 hour) vital signs will be measured at minute 0, 15, 30, 45, and 60.
 - Post infusion, vital signs will be measured at minute 90 and 120.
6. Follow study procedures as described in the schedule of assessments of the visit.

Investigational Product Assignment (Randomization and Blinding)

A total of 24 eligible subjects will be randomized to either placebo (approx. 12) or active drug (approx. 12) (HB-adMSCs) in a 1:1 balanced design. The randomization will be applicable only to eligible subjects. If a subject is not eligible during the screening process for study participation, this subject shall not be randomized to any group.

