If an infusion is stopped for a subject due to an adverse event or serious adverse event, including but not limited to hypersensitivity reaction/anaphylaxis, no additional study treatment will be given to the study participant who develops the event. Although, the study participant will not receive the investigational product, he or she must be followed for safety purposes according to the protocol.

Study Stopping Rules

This Clinical Trial will stop if any of the following events are present:

1. Subject's Death.
2. Occurrence of any thromboembolic event during or after HB-adMSCs administrations (up to 72 hours).
3. Any cerebrovascular ischemia or seizure event occurring within 72 hours after any of the investigational product administrations.
4. Any Serious Adverse Events determined to be related to the following:

- When there is one CTCAE.v5 grade 4 or 5 AE, irrespective of attribution.
- Either any CTCAE Grade 2 adverse event that persists for more than two weeks, or any Grade 3 adverse event, that occurs within 72 hours after product administration.

Should the study participant discontinue study treatment he/she will be followed for safety according to the protocol safety monitoring plan. The study participant will receive follow up communication via phone calls and/or electronically to ascertain the outcome until resolved fully. All will be documented as per protocol.

All changes to the study stopping rules shall be reviewed by FDA. If the study is suspended for any reason, it will not be re-opened until FDA agrees. Regardless of whether the study is stopped or suspended all subjects will be followed to the EOS as per protocol.

Statistical Methods

Sample size consists of up to 24 subjects who have been diagnosed with Relapsing Remitting Multiple Sclerosis. All data collected from subjects who are enrolled and received the investigational product will be analyzed. The incidence of Adverse Events and Serious Adverse Events will be recorded and reported. Efficacy will be measured by improvement of subject's signs and symptoms associated with Multiple Sclerosis. Interim analysis of all safety and efficacy data may be performed at any time deemed appropriate by the Sponsor. Although, the subject's data may be analyzed at any time, a data analysis of all available data will be conducted when a least 10 subjects in each group have completed Week 24. Data may be analyzed for internal informational purposes, reports, presentations, and manuscripts.

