## 2.2. Study Design

Overview of Study Design and Key Features	
	<pre> graph TD     Screening[Screening] --> Eligible{Eligible}     Eligible -- No --> ScreeningFailure[Screening Failure]     Eligible -- Yes --> Randomization[Randomization]     Randomization --> Week0[Week 0 (Baseline)]     Week0 --> Week4[Week 4 INF # 2]     Week4 --> Week8[Week 8 INF # 3]     Week8 --> Week16[Week 16 INF # 4]     Week16 --> Week24[Week 24 INF # 5]     Week24 --> Week32[Week 32 INF # 6]     Week32 --> Week42[Week 42 Follow Up]     Week42 --> Week52[Week 52 EOS]   </pre>
Design Features	
This study will be a randomized, double-blind, single center, phase 2 study to assess efficacy and safety of multiple HB-adMSCs vs. Placebo for the treatment of Multiple Sclerosis. The trial includes,
 
 
• A screening period of up to 4 weeks
 
• A 32-week treatment period while on randomized study treatment 
 
▪ Infusion 1 (Week 0), Infusion 2 (Week 4), Infusion 3 (Week 8), Infusion 4 (Week 16), Infusion 5 (Week 24) and Infusion 6 (Week 32)
 
 
 
• A safety Follow-up period of 20 weeks after the last investigational product administration. 
 
▪ Follow up at week 42 and end of study at Week 52
 
 
 
• 24 Subjects
 
• 2 Treatment groups 
 
▪ Group 1 → HB-adMSCs
 
▪ Group 2 → Placebo
 
 
 

Study Intervention	
 
• Active Product: HB- adMSCs (Hope Biosciences adipose derived mesenchymal stem cells) 
 
▪ Dose: 200 million
 
▪ Route: Intravenous
 
▪ Regimen: Weeks 0, 4, 8, 16, 24 and 32.
 
 
 
• Placebo: Saline Solution 0.9% 
 
▪ Dose: N/A
 
▪ Route: Intravenous
 
▪ Regimen: Weeks 0, 4, 8, 16, 24 and 32.
 
 
 
• Duration of administration 1 hour
 
• Study treatment details,
 

Overview of Study Design and Key Features		

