	<pre> graph TD     subgraph Placebo_Path [Placebo]         direction TB         M[Manufacturer] --- BE[Baxter or an equivalent manufacturer]         BE --- D[20 ml sterile saline]         D --- R[Intravenous]         R --- AR[4-5 ml/min]         AR --- P[Preparation]         P --- PS[Placebo will contain 20 ml of sterile saline. Placebo should be diluted in 250 ml of 0.9% Sodium chloride.]     end      subgraph HBadMSCs_Path [HB-adMSCs (autologous)]         direction TB         H[Hope Biosciences] --- D2[2 x 10^8 ± 20% cells suspended in 20 ml sterile saline]         D2 --- R2[Intravenous]         R2 --- AR2[4-5 ml/min]         AR2 --- P2[Preparation]         P2 --- PS2[Syringe will contain 20 ml of autologous HB-adMSCs. HB-adMSCs should be diluted in 250 ml of 0.9% Sodium chloride.]     end </pre>	
Study Intervention Assignment	
 
Participants will be randomised 1:1 to receive HB-adMSCs active treatment or Placebo.
 
	
Interim Analysis	
 
No interim analysis will be performed in this study
 
	

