#### **7.1.5. Study Intervention Exposure and Compliance**

A summary of Overall cumulative exposure to HB-adMSCs will be produced.

The details of the planned displays are in programming specification document.

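### The SAP's exposure formula gives zero weeks to a participant dosed once and cannot show how many infusions were received

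*SAP*

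**What the plan says.** SAP 5.3.2.1 (Extent of Exposure) opens with "Number of days of exposure to study drug will be calculated based on the formula". The formula that follows is "Duration of Exposure in Weeks = (Treatment stop date – Treatment start date)/7". Neither document defines the treatment stop date. The same section adds: "Participants who were randomized but not report a treatment start date will be categorised as having zero days of exposure".

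Treatment is intermittent. SAP 2.2 gives "Regimen: Weeks 0, 4, 8, 16, 24 and 32", and the protocol's administration instructions say "Administer the infusion solution over a period of 1h (infusion rate 4-5ml/min". The protocol's Treatment Regimen section puts the treatment duration at 32 weeks with six doses.

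Both documents allow for a course that ends after one infusion. Under the protocol's Infusion Stopping Rules, if an infusion is stopped for an adverse event, "no additional study treatment will be given to the study participant who develops the event". The Investigational Plan arranges follow-up for participants who leave after a single treatment.

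The only other exposure summary is in SAP 7.1.5: "A summary of Overall cumulative exposure to HB-adMSCs will be produced". No unit or formula is given there, and placebo is not mentioned. SAP 5.3.2.1 and 7.1.5 both leave display details to a programming specification that is not among the documents.

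**The concern.** The formula suits a drug taken daily, where the span from first to last dose is close to the time on treatment. Here each dose is a one-hour event, and the span between the first and last event is a different quantity from the amount of treatment received. Two things follow.

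- A course of one infusion has no span, so a dosed participant is recorded with no exposure.
- A span does not determine how many infusions lie within it.

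The participant most likely to have a one-infusion course is one stopped for a reaction at the first infusion. Hypersensitivity is an adverse event of special interest in this trial, so an exposure table that shows such a person at zero misdescribes the case a safety reader would want to see clearly.

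**Working it through.** **Inputs**
- Infusions at Weeks 0, 4, 8, 16, 24 and 32 (SAP 2.2), each lasting one hour, so each starts and ends on one date.
- Formula: (stop − start)/7, with no added day (SAP 5.3.2.1).
- Study day on or after Day 1 = reference date − Day 1 date + 1 (SAP 7.2.3).
- Assumption: the stop date is the date of the last infusion.

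**The plan's own figure.** Infusion 6 falls on day 32 × 7 = 224 after infusion 1, and (224 − 0)/7 = 32.0 weeks. This is the stated treatment duration, which supports the assumption about the stop date.

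**Same formula for shorter courses, infusions given in sequence**

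| Infusions received | Days from first to last | SAP formula (weeks) | With + 1 day |
|---|---|---|---|
| 1 | 0 | 0.0 | 1 day (0.14 weeks) |
| 2 | 28 | 4.0 | 29 days (4.14 weeks) |
| 3 | 56 | 8.0 | 57 days (8.14 weeks) |
| 4 | 112 | 16.0 | 113 days (16.14 weeks) |
| 5 | 168 | 24.0 | 169 days (24.14 weeks) |
| 6 | 224 | 32.0 | 225 days (32.14 weeks) |

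**The zero against the rest of the SAP**
- SAP 4 puts anyone who received at least one dose in the Safety set.
- SAP 5.3.2.2 treats the day of the first infusion as the first day of exposure and counts events from that day as treatment-emergent. A one-infusion participant can therefore have treatment-emergent events with zero exposure. (The flag table in SAP 7.2.2 runs the other way; that is a separate matter, and 5.3.2.2 is used here.)
- SAP 7.2.3 would count the same day as Day 1, not Day 0.

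**Number of infusions.** A participant with the first and the Week 32 infusion gets 224/7 = 32.0 weeks whatever happened in between. Adding a day gives 32.14 weeks in every such case, so the added day separates one infusion from none but does not make the measure a count.

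**Sensitivity**
- If the stop date were instead the follow-up visit about 30 days after a single infusion, that participant would get 30/7 = 4.3 weeks and not 0.
- Assuming the ±7-day visit window applies to infusion 6 only, the full course runs from 217/7 = 31 to 231/7 = 33 weeks. If it applies at both ends, the range is 30 to 34 weeks. The 32 weeks is therefore nominal.

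**The case against.** The strongest reply is that the formula is labelled a duration, it reproduces the planned 32 weeks, and duration is not dose. Cumulative exposure is a separate planned summary, and the unseen programming specification may give its layout. This stands as far as it goes: one cannot say that dose received will go unreported, only that the SAP does not define how. It does not rescue a zero for someone who was dosed.

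A reader might also infer more than the documents support:

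- **That one-infusion and never-dosed participants will be mixed in the safety tables.** Safety analyses use the Safety set, which requires a dose, and study population analyses default to it. The shared zero can arise only in the derivation or in a listing of all randomised participants.
- **That adverse event results will be distorted.** SAP 5.3.2.2 reports numbers of participants, percentages and event counts. No rate uses exposure time as a denominator, and a participant stopped at the first infusion counts fully.
- **That the fall in an arm's mean shows the error.** One first-infusion stop among 12 lowers the mean from 32.0 to (11 × 32 + 0)/12 = 29.3 weeks. With the added day it falls from 32.14 to (11 × 32.14 + 0.14)/12 = 29.48, the same drop of 2.67 weeks. That drop reflects early stopping, which a duration should show.
- **That participants will have only infusions 1 and 6.** Six doses are planned, and an infusion stopped for an adverse event ends treatment. The documents do not describe missing four infusions and resuming. The case shows what the formula cannot distinguish and is not a forecast.
- **That the cell tolerance must enter the exposure measure.** SAP 2.2 gives "2 x 10^8 ± 20% cells suspended in 20 ml sterile saline", so six full infusions could total 6 × 160 = 960 to 6 × 240 = 1,440 million cells. The documents do not show that released counts or the fraction of a bag infused are collected for analysis, so this cannot be made a requirement.

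**Conclusion.** The concern holds as a defect in descriptive safety reporting. With the stop date read as the last infusion, the stated rule returns 0 weeks for a dosed participant in a situation the protocol foresees, and this disagrees with the SAP's own first day of exposure and inclusive day count. The missing day amounts to one day (0.14 weeks) per participant; it matters because it is the difference between some exposure and none. Three related gaps stand beside it: the undefined stop date, which moves the one-infusion result between 0 and about 4.3 weeks; the mismatch between days and weeks; and the absence of any defined infusion count or cumulative measure covering both arms. No efficacy test, treatment estimate or adverse event percentage depends on the value. The zero rests on the last-infusion reading, which the SAP does not state but which its 32 weeks supports.

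**What to change.** In SAP 5.3.2.1 and 7.1.5:

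1. Make the number of infusions started and the number completed per participant, summarised by arm, the main exposure measure. State what counts as completed. The Efficacy set already depends on who received all six, so one definition should serve both.
2. Define the treatment stop date as the date of the last infusion.
3. If calendar time is kept, label it time from first to last infusion, calculate it as (last − first + 1) days, and use one unit in the text, formula and table.
4. List never-dosed randomised participants separately, without assigning them a duration that enters a summary.
5. Define the summary in 7.1.5 and cover both arms (infusions for placebo). Cumulative cells in the active arm may be added if released cell counts are available; this is optional.

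The cost is minor SAP wording and one derived count. The protocol already requires infusion start and end times, with comments where needed, in the source documents. Only the optional cell total might need further data.

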### **5.3.2.2. Adverse Events**

AEs will be coded using the most recent version of the Medical Dictionary for Regulatory Activities (MedDRA).

A treatment emergent adverse event (TEAE) is defined as an event that has onset date on or after the first day of exposure to infusion treatment and on or before the first safety follow up at week 42/early withdrawal date. Here the first day of exposure is defined as the first day of exposure to infusion treatment.

Treatment emergent Adverse events TEAEs are summarized descriptively, whereas non-TEAEs are presented in listings. TEAE data will be displayed in terms of the number of subjects with at least one event (N), percentage of subjects with at least one event (%) and the number of events (E).

Summaries of TEAEs and of serious AEs will be presented as an overview including all AEs, serious AEs, AEs by severity, AEs by relation to treatment, action to AEs and treatment advised, and outcome of AEs.

Furthermore, summary tables based on system organ class and preferred terms are made for:

- All TEAEs
- Serious AEs
- AEs leading to withdrawal of study
- Incidence and risk of AEs of special interest (serious or nonserious), including thromboembolic events, peripheral events defined as, thromboembolism of the extremities, also infections and hypersensitivities.

Individual adverse events will be listed.

The details of the planned displays are in programming specification document.

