A complete physical examination will be performed by the principal investigator or delegated sub-investigator, including general appearance, head, eyes, ear, nose, and throat (HEENT), neck, cardiovascular, thorax/lungs, abdomen, genitourinary, musculoskeletal, lymph nodes, skin, neurological and mental status examination, height (at Screening only), and body weight at Visits 1, 2, 3, 4, 5, 6, 7, 8 and 9.

The principal investigator or delegated sub-investigator will evaluate the clinical significance of abnormal findings identified during physical examinations. Pre-existing conditions diagnosed through assessments and examinations at the screening visit or during the screening period are not adverse events but are recorded as medical history. If any clinically significant abnormal findings are discovered after informed consent or any pre-existing conditions worsen during the trial, these must be recorded as adverse events.

Vital Signs

Vital signs will be measured at Visits 1, 2, 3, 4, 5, 6, 7, 8 and 9 and will include respiratory rate, pulse rate, blood pressure (measured after the study participant has been in a seated position for more than 5 minutes of rest), body temperature and oxygen saturation. Clinical significance of any abnormal result must be evaluated by principal investigator. Clinically significant abnormal findings will be reported as adverse events.

Clinical Safety Laboratory Parameters

The following laboratory parameters should be collected at Visit 1, 2, 6 and 9.

- Comprehensive Metabolic Panel, also known as CMP or Chemistry Panel is a group of different tests that measure several substances in the study's participant blood. The following tests are included in this panel:

Comprehensive Metabolic Panel (CMP)	Reference Range	Units
GLUCOSE	70-99	MG/DL
BUN	6-20	MG/DL
CREATININE	0.60-1.30	MG/DL
eGFR AFRICAN AMER.	>60	ML/MIN/1.73
eGFR NON-AFRICAN AMER.	>60	ML/MIN/1.73
CALC BUN/CREAT	6-28	Ratio
SODIUM	133-146	MEQ/L
POTASSIUM	3.5-5.4	MEQ/L
CHLORIDE	95-107	MEQ/L
CARBON DIOXIDE	19-31	MEQ/L
CALCIUM	8.5-10.5	MG/DL
PROTEIN, TOTAL	6.1-8.3	G/DL
ALBUMIN	3.5-5.2	G/DL
CALC GLOBULIN	1.9-3.7	G/DL
CALC A/G RATIO	1.0-2.6	Ratio
BILIRUBIN, TOTAL	<=1.2	MG/DL
ALKALINE PHOSPHATASE	40-114	U/L
AST	9-40	U/L
ALT	5-40	U/L

- Complete Blood Count, also known as CBC, hemogram or CBC with Differential is a group of tests that evaluate the cells that circulate in blood, including red blood cells (RBCs), white blood cells (WBCs), and platelets.

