Unanticipated Problems Involving Risk to Subjects or Others

Any incident, experience, or outcome that meets all the following criteria:

- Unexpected in nature, severity, or frequency (i.e., not described in study-related documents such as the IRB-approved protocol or consent form, the investigators brochure, etc.)
- Related or possibly related to participation in the research (i.e., possibly related means there is a reasonable possibility that the incident experience, or outcome may have been caused by the procedures involved in the research.)
- Serious (as defined below) ***“Serious” is different than “severe” as reported in the CTC criteria that applies a grade to the AE.***

Adverse Event

An ***adverse event*** (AE) is any symptom, sign, illness, or experience that develops or worsens in severity during the study. Intercurrent illnesses or injuries should be regarded as adverse events. Abnormal results of diagnostic procedures are adverse events if the abnormality:

- results in study withdrawal
- is associated with a serious adverse event
- is associated with clinical signs or symptoms
- leads to additional treatment or to further diagnostic tests
- is considered by the investigator to be of clinical significance

Serious Adverse Event

Adverse events are classified as serious or non-serious. A ***serious adverse event*** is any AE that is:

- fatal
- life-threatening
- requires or prolongs hospital stay
- results in persistent or significant disability or incapacity
- a congenital anomaly or birth defect
- an important medical event

Important medical events are those that may not be immediately life threatening but are clearly of major clinical significance. They may jeopardize the subject and may require intervention to prevent one of the other serious outcomes noted above. For example, drug overdose or abuse, a seizure that did not result in in-patient hospitalization, or intensive treatment of bronchospasm in an emergency department would typically be considered serious.

All adverse events that do not meet any of the criteria for serious should be regarded as ***non-serious adverse events***.

Adverse Event Reporting Period

The study period during which adverse events must be reported is normally defined as the period from the initiation of any study procedures to the end of the study treatment follow-up. For this study, the study treatment follow-up is defined as approximately 20 weeks following the last administration of study treatment.

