Recording of Adverse Events

At each contact with the subject, the investigator must seek information on adverse events by specific questioning and, as appropriate, by examination. Information on all adverse events should be recorded immediately in the source documents and CRF and in the appropriate adverse event section of the source documents. All clearly related signs, symptoms, and abnormal diagnostic procedures results should be recorded in the source document and CRF, though should be grouped under one diagnosis.

All adverse events occurring during the study period must be recorded. The clinical course of each event should be followed until resolution, stabilization, or until it has been determined that the study treatment or participation is not the cause. Serious adverse events that are still ongoing at the end of the study period must be followed up to determine the outcome. Any serious adverse event that occurs after the study period and is possibly related to the study treatment or study participation should be recorded and reported immediately.

Reporting of Serious Adverse Events and Unanticipated Problems.

Investigator and the Sponsor must follow reporting timelines if any Serious Adverse Event or Unanticipated Problem occurs to the subject. Also, if any of them have the following criteria, it must be reported in a timely manner:

- related to study participation
- unexpected
- serious or involve risks to subjects or others

This report should include the minimum necessary information provided in the following table:

Stopping Rules

Infusion Stopping Rules

Study treatment infusion will be stopped if a least one of the following events occur:

1. Allergic reaction as evidenced by severe dyspnea (defined as intense tightening of chest, air hunger, breathlessness or feeling of suffocation), bronchospasm (defined as coughing, wheezing, difficulty breathing) or hypoxia (defined as pulse oximeter reading of less than 90%) after the product has been administered intravenously.
2. Patient verbally decline the treatment at any moment prior, or during the infusion.
3. Hyperpyrexia develops after infusion administration begins (core body temperature greater than or equal to 104°F).
4. Principal Investigator may stop the infusion at any time, based upon PI's discretion.
5. Malignant Hypertension (180/120 mm/Hg)
6. Sudden Severe Hypotension (30-40 mm/Hg drop from pre-infusion level)

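### The SAP defines treatment-emergent events by onset date alone, so an event that starts before the first infusion and worsens after it may be missing from the TEAE summaries

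*SAP*

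**What the plan says.** The protocol, under Adverse Event, defines an adverse event as one that "is any symptom, sign, illness, or experience that develops or worsens in severity during the study". Under Adverse Event Reporting Period, reporting covers "the period from the initiation of any study procedures to the end of the study treatment follow-up". That includes a screening period of up to 28 days before infusion 1.

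Under Physical Examinations, the protocol treats conditions found in screening as medical history: "Pre-existing conditions diagnosed through assessments and examinations at the screening visit or during the screening period are not adverse events". The same paragraph adds that if "any pre-existing conditions worsen during the trial, these must be recorded as adverse events". It does not say what onset date that record should carry.

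SAP 5.3.2.2 defines a TEAE as "defined as an event that has onset date on or after the first day of exposure to infusion treatment". The window closes at the Week 42 visit, or earlier if the participant withdraws. On reporting it says: "Treatment emergent Adverse events TEAEs are summarized descriptively, whereas non-TEAEs are presented in listings". The section also plans tables for serious AEs, AEs leading to withdrawal and AEs of special interest, and the titles of these tables do not restrict them to TEAEs.

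SAP 7.2.2 gives a second rule, also based on start date only. It assigns Y to events that start before the first dose. It assigns N to events that start on or after it, and to events with a missing or partial date.

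**The concern.** The protocol's definition of an adverse event has two limbs, new onset and worsening. The TEAE rule keeps only the first. If a problem is on record as an adverse event before infusion 1 and becomes more severe afterwards, its onset date still precedes dosing, and the rule sends it to the listings.

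The protocol names TEAE incidence among both its primary and its secondary endpoints, and SAP 2.1 lists it as a secondary endpoint. Aggravation of an existing problem is one form that harm from an infusion could take. As written, whether it is counted depends on how site staff happen to enter it. A pre-specified rule should remove that dependence. With so few participants per arm, one record handled differently is visible in a table.

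**Working it through.** The plan gives no figure to reproduce. The check traces one case through the stated rules: a problem that starts in screening and worsens after an infusion, before Week 42.

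**Can such a record exist?** Yes. The protocol's reporting period opens at the first study procedure. The SAP also expects pre-dose events, because 5.3.2.2 provides listings for non-TEAEs and the date rules in 7.2.6 handle events that stop before study treatment starts.

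**How might it be recorded?** The documents leave two ways open:

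- (a) one record that keeps its screening onset date, with the severity updated;
- (b) a new adverse event dated at the worsening.

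The protocol requires worsening of a pre-existing condition to be recorded as an adverse event but fixes no onset date. For an adverse event already open at first dose, neither document requires (b).

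**What does each SAP rule do with it?**

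| Rule | (a) screening onset kept | (b) new AE dated at worsening |
|---|---|---|
| SAP 5.3.2.2 | Not a TEAE; listing only | TEAE; tabulated |
| SAP 7.2.2, read literally | Y | N |

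Under 5.3.2.2 the outcome turns entirely on the recording choice. Under 7.2.2 it turns on the same choice with the opposite result, because that table's two definitions are reversed. Once 7.2.2 is corrected to agree with 5.3.2.2, cell (a) becomes a non-TEAE under both rules, so correcting the reversal does not close the gap.

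**How much does one participant weigh?** The protocol's randomization section gives about 12 per arm. One participant is 1/12 = 0.083, or about 8.3 percentage points of one arm's incidence for one term. This holds only if that participant has no other TEAE with the same term; otherwise they are already counted and the incidence does not move.

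**How often would it happen?** The documents give no rate for events that are open at first dose and later worsen. Any probability of at least one such case among the 24 participants would only restate an assumed rate, so none is given.

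**The case against.** The strongest reply is that the protocol already covers most of this. Worsening is itself an adverse event by definition, and worsening of a pre-existing condition must be recorded as one. It is natural to date that event from when the worsening began. After an infusion and up to Week 42, it would then satisfy 5.3.2.2 and be tabulated. Chronic MS symptoms present at entry are medical history and follow this route. What remains is mainly an event that arises in screening, is still open at infusion 1, worsens later and is not entered again. That group is probably small: Table 4 schedules no adverse event assessment at Visit 1, and the Visit 1 procedures list none.

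Much of this stands, and it limits the point in three ways.

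- A reader might infer that every pre-dose event that worsens is lost from every TEAE table. The documents do not support that, because an event dated at the worsening is counted.
- A reader might take the protocol's instruction on related findings, "though should be grouped under one diagnosis", as forcing worsening onto the old record. It concerns signs, symptoms and test results belonging to one illness. It says nothing about change in severity over time.
- A reader might infer that serious worsening is hidden. The tables for serious AEs, withdrawals and special-interest AEs are not expressly limited to TEAEs, so such events have a plausible route into a table. The wording is ambiguous beside the sentence that sends non-TEAEs to listings. Non-serious worsening that does not lead to withdrawal and is not of special interest has no such route.

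The reply does not remove the gap. Dating from the worsening is a natural reading but not a stated rule, and for an adverse event already open at first dose no instruction exists.

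**Conclusion.** The point holds as a gap in specification. SAP 5.3.2.2 has no worsening criterion, although the protocol's adverse event definition has one and reporting starts before dosing. A pre-dose event that worsens after an infusion may be left out of the TEAE summaries, depending on a recording choice that neither document settles.

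The total effect cannot be sized from the documents. One affected participant changes a term's incidence in one arm by about 8 percentage points, assuming about 12 per arm and no other TEAE with that term for that participant. A reader might go further and infer a biased comparison between arms. The documents do not show that, because they give no event rates and no reason to expect the recording choice to differ by arm.

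The reversal in SAP 7.2.2 is the larger defect of the two, since read literally it misclassifies ordinary post-dose events as well. It is raised here because both rules need the same worsening criterion and must agree.

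**What to change.** 1. In SAP 5.3.2.2, keep the onset rule and add that an event with onset before the first infusion also counts as a TEAE if it increases in severity or becomes serious on or after the first infusion. Date it at the worsening and apply the same end of window.
2. State, in the SAP and in the CRF completion instructions, that such worsening is recorded as a new adverse event with that date. Link it to the pre-dose record so that it is counted once.
3. Correct SAP 7.2.2 so that its Y and N definitions match 5.3.2.2, including the worsening criterion. Swapping the two labels alone would leave that criterion out.
4. State whether the tables for serious AEs, AEs leading to withdrawal and AEs of special interest are restricted to TEAEs.

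The cost is a few sentences in the SAP and one recording instruction, with no new assessments. The downside is small: a few more events enter the TEAE tables.
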